## 11 SOFTWARE

All statistical analyses will be performed using SAS® version 9.4 or higher.

The PK parameters will be calculated using WinNonlin® software (version 6.3 or later).

## Appendix 1 Pharmacokinetic Parameter Calculations

Actual blood sampling times will be used in the calculation of pharmacokinetic parameters

All concentrations below the LLOQ will be set at zero for pharmacokinetic calculations

When Kel is missing (or cannot be determined),  $t_{1/2}$ ,  $AUC_{0-\infty}$ ,  $AUC\%_{ex}$ , CL/F, MRT, Vz/F and Vss/F will not be calculated.

PK Parameter Calculations		
Parameters	Unit	Calculation
$C_{max}$	ng/mL	will be determined by visual inspection
$AUC_{0-\infty}$	ng·h/m L	$AUC_{0-\infty} = AUC_{0-last} + AUC\%_{ex}$
$AUC\%_{ex}$	ng·h/m L	$AUC_{exp} = C_{last} / Kel$ $C_{last}$ : last measurable concentration
$AUC_{0-last}$	ng·h/m L	will be calculated using the linear trapezoidal method and actual times $AUC_{0-la} = \sum_{i=1}^n \frac{t_i - t_{i+1}}{2} (C_{i-1} + C_i)$
$t_{max}$	h	Measured time of $C_{max}$
$t_{1/2}$	h	$t_{1/2}$ will be determined as: $t_{1/2} = \log_e (2) / Kel$
Kel	/h	
The exponential rate constant of the terminal phase, Kel, will be estimated by log-linear regression, if determinable. The number of data points included in the regression will be determined by visual inspection. Wherever possible, a minimum of 3 data points will be used in the estimation of Kel.
 
During the analysis, this calculation method repeats regressions using the last three points with non-zero concentrations, then the last four points, last five, etc. The time of maximum concentration (tmax) will be excluded from the estimation of Kel.
 
Points with a value of zero for the dependent variable are excluded.
 
For each regression, an adjusted <math>R^2</math> is computed
 $Adjusted R^2 = 1 - \frac{(1 - R^2) \times (n - 1)}{(n - 2)}$

		
where n is the number of data points in the regression and <math>R^2</math> is the square of the correlation coefficient.
 
The regression with the largest adjusted <math>R^2</math> is selected to estimate <math>K_{el}</math>, with these caveats:
 
 
- If the adjusted <math>R^2</math> does not improve, but is within 0.0001 of the largest adjusted <math>R^2</math> value, the regression with the larger number of points is used.
 
- <math>K_{el}</math> must be positive, and calculated from at least three data points.
 

CL/F	L/h	$CL/F = Dose / AUC_{0-\infty}$
MRT	/h	$MRT = AUMC_{0-\infty} / AUC_{0-\infty}$ AUMC 0-∞ : area under the first moment curve extrapolated to infinity
Vz/F	L	$Vz/F = CL/F \times 1/K_{el}$
Vss/F	L	$Vss/F = CL/F \times MRT$
LF	-	$LF = AUC_{0-\tau}[\text{Day 14}] / AUC_{0-\infty}[\text{Day 1}]$
RA	-	$RA = AUC_{0-\tau}[\text{Day 14}] / AUC_{0-\tau}[\text{Day 1}]$

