## 1. INTRODUCTION

This statistical analysis plan (SAP) is based on the final protocol (v2.0) dated 12-DEC-2018. The plan covers statistical analysis, tabulations and listings of the study data to investigate the safety, tolerability and pharmacokinetics of single and multiple ascending doses of MT-6345 compared to placebo in healthy subjects.

Any statistical analysis details described in this document supersede any description of statistical analysis in the protocol.

This study was terminated due to brain changes in male rats in the 13-week tox study. Subjects were enrolled in only Part 1, Part 2 and Part 3. Some assessments which were not performed are grayed out in this SAP.

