## 2.2.2. Secondary Endpoints

### Pharmacokinetic assessments:

Plasma concentration versus time profile of MT-6345 after single and multiple dosing.

The following PK parameters will be calculated for MT-6345 after single dosing:

- Maximum plasma concentration after administration ( $C_{max}$ )
- Time to maximum plasma concentration ( $t_{max}$ ).
- Plasma terminal elimination half-life- ( $t_{1/2}$ ).
- Area under the plasma concentration-time- curve from time zero to 24 hours ( $AUC_{0-24h}$ ).
- Area under the plasma concentration-time- curve from time zero to the last measurable concentration ( $AUC_{0-last}$ ).
- Area under the plasma concentration-time curve from zero up to infinity with extrapolation of the terminal phase ( $AUC_{0-\infty}$ )
- Terminal elimination rate constant (Kel).
- Mean residence time (MRT).
- Apparent oral clearance (CL/F).
- Apparent volume of distribution during terminal phase ( $Vz/F$ )
- Apparent volume of distribution at steady state ( $Vss/F$ )

The following PK parameters will be calculated for MT-6345 after multiple dosing where appropriate:

- $C_{max}$ .
- $t_{max}$ .
- $t_{1/2}$ .
- Area under the plasma concentration-time- curve over the dosing interval ( $AUC_{0-\tau}$ ).
- $AUC_{0-last}$ .
- $AUC_{0-\infty}$ .
- Kel.
- MRT.
- CL/F.

- Apparent volume of distribution at steady state ( $V_{ss}/F$ ).
- Apparent volume of distribution during terminal phase ( $V_z/F$ )
- Linearity factor (LF).
- Accumulation ratio (AR).
- Urinary excreted amount of test compound (Ae).
- Urinary excreted amount of test compound expressed as a percentage of the dose administered (Ae%).
- Renal clearance ( $CL_R$ ).

QT interval assessments

Continuous 12-lead Holter data will be obtained from subjects in Parts 1 and 3. Data will be analysed following completion of the study to investigate the potential effect of MT-6345 on QTc interval or stored for future analysis.

2.2.3. [REDACTED]

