**Table 2 Time and events schedule for Part 3**

Study Day	SCR	Treatment day	FU
	-28 to -3	Day -2 to maximum of Day 31 (confinement period)	5 and 8 days after last dose
Outpatient visit	X		X
Informed consent	X		X
Demography and medical history	X		
Inclusion/exclusion criteria	X		
Body weight and BMI	X		
Height	X		
Drug and alcohol screening 	X		
Serology 	X		
Physical examination 	X		
Eye examination 	X		
Supine blood pressure, pulse and respiratory rate	X		
Oral body temperature	X		
12-lead ECG (safety)	X		
Haematology, biochemistry, coagulation and urinalysis	X		
Blood sampling for PK 			
Adverse events			
Concomitant medication			

Abbreviations: BMI=body mass index; ECG=electrocardiogram; PK=blood sample for PK; FU=Follow-up Visit; HIV=human immunodeficiency virus; SCR=Screening Visit.

1. Urine drugs of abuse screen will include tests for methadone, cocaine, tetrahydrocannabinol, benzodiazepines, barbiturates, amphetamines and opiates. Carbon monoxide and alcohol breath tests will also be performed.

2. Serology testing for hepatitis B surface antigen, hepatitis B core antibody, hepatitis C antibodies and HIV 1/2 antibodies.

3. Full physical examination will be performed at Screening and Follow-up. At other times, a targeted (symptom driven) physical examination of relevant body system(s) will be performed following physician assessment if the subject reports feeling unwell or an adverse event.

4. Conducted by a Consultant Ophthalmologist. Further details can be found in Section 6.5.1. Screening examination may be performed at any time between Day -28 and Day -3. Follow-up examination may be performed at any time between last dosing and the Follow-up Visit.

5. PK blood samples for MT-6345 will be collected during the confinement period (see Table 3). Subjects will return for outpatient visits and PK blood samples will be taken 5 and 8 days after the last dose (120 and 192 hours after the last dose), and at FU 14 ± 1 days after last dose (336 hours after last dose).

Confidential

Page 17 of 38

**Table 3** Time and events schedule for Part 3 (confinement period)

Study Day	ADM	Treatment day													
		1	2	3	4	5	6	7	D 	8	9	10	11	12	13
Time point (hours)	Pre	0	0.5	1	1.5	2	3	4	5	6	7	48	72	96	120
Blood sampling for PK 	X	X	X	X	X	X	X	X	X	X	X	X	X	X	X
Urine sampling for PK 	█	█	█	█	█	█	█	█	█	█	█	█	█	█	█
Adverse events															

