### 8.3.2. Pharmacokinetic Parameters

The pharmacokinetic parameters listed in Section 2.2 will be calculated for each subject on active dose using a non-compartmental model. The pharmacokinetic parameters will also be listed. The plasma pharmacokinetic parameters will be summarized by each dose group and fed state. The plasma pharmacokinetic parameters will also be listed for each part.

The urinary pharmacokinetic parameters will be summarized for each dose level. The urinary pharmacokinetic parameters will also be listed.

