## 10 CHANGE FROM THE PROTOCOL

The planned analyses below were not done.

- Summary of AEs by SOC, Preferred Term and severity of event
- Summary of the change from baseline for vital signs, 12-lead ECG and routine safety laboratory tests
- A linear mixed model analysis for log-transformed PK parameters
- All analyses for Part 4 or 5

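### SAP Appendix 1 gives CL/F, MRT, Vz/F and Vss/F only in single-dose (AUC0-inf) form, without saying so, although SAP 2.2.2 also lists them after multiple dosing (minor)

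*SAP*

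**What the plan says.** SAP 2.2.2 has two parameter lists. CL/F, MRT, Vz/F and Vss/F are in the single-dose list and again in the second list, which opens "The following PK parameters will be calculated for MT-6345 after multiple dosing where appropriate". SAP 8.3.2 then says: "The pharmacokinetic parameters listed in Section 2.2 will be calculated for each subject on active dose using a non-compartmental model".

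Appendix 1 has one row for each of the four:

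- CL/F = Dose / AUC0-inf
- MRT = AUMC0-inf / AUC0-inf
- Vz/F = CL/F × 1/Kel
- Vss/F = CL/F × MRT

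None carries a day or a regimen. The LF and RA rows of the same table do carry Day 14 and Day 1 labels, so the table also serves multiple dosing. If Kel cannot be determined, "CL/F, MRT, Vz/F and Vss/F will not be calculated". AUC0-tau is a listed multiple-dose parameter but enters only LF and RA. SAP 7.1.3.2, SAP 8.3.2 and Protocol 10.3.5.3 give no other formula.

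On what was actually done, SAP 1 says the study was terminated and that "Some assessments which were not performed are grayed out in this SAP". SAP 3.3.2 gives 8 subjects in Part 3 and does not state the number of doses. SAP Table 2 times the Part 3 follow-up as "FU 14 ± 1 days after last dose (336 hours after last dose". The Part 3 tables in SAP 7.2 and 9.3 place that visit at Day 15.

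**The concern.** Dose / AUC0-inf is a clearance only if all the drug under the curve came from that dose. After a second or later dose, the curve from the last dose to infinity also contains what remained from the preceding doses. The denominator is then too large, so CL/F is too low even when kinetics are linear, and Vz/F falls in the same proportion. MRT and Vss/F can move as well, by an amount and in a direction that depend on the shape of the profile.

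A reader comparing Day 1 with last-dose values in the first human data on this compound could take such a drop for a real change in clearance.

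**Working it through.** The plan states no figure to reproduce. The check applies the Appendix 1 rows to a linear-kinetics profile after n daily doses and compares the result with the true value.

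**Inputs.** The dosing interval is 24 h (once daily, SAP 3.1.1, Part 3). The visible documents give no half-life for MT-6345, so 6, 12, 24 and 48 h are assumed.

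**CL/F and Vz/F.** Take one compartment with rapid absorption, and let q = 2^(−24/t½) be the fraction left after 24 h. After n doses the profile is the single-dose profile multiplied by (1 − q^n)/(1 − q), and so is AUC0-inf. Hence

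written / true CL/F = (1 − q)/(1 − q^n).

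Kel does not change, so the same ratio holds for Vz/F. The ratio is 1 for n = 1, 1/(1 + q) for n = 2 and 1/(1 + q + q²) for n = 3.

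| t½ (h) | q | 1 dose | 2 doses | 3 doses |
|---|---|---|---|---|
| 6 | 0.0625 | 1.00 | 1/1.0625 = 0.94 | 1/1.0664 = 0.94 |
| 12 | 0.25 | 1.00 | 1/1.25 = 0.80 | 1/1.3125 = 0.76 |
| 24 | 0.50 | 1.00 | 1/1.50 = 0.67 | 1/1.75 = 0.57 |
| 48 | 0.7071 | 1.00 | 1/1.7071 = 0.59 | 1/2.2071 = 0.45 |

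Adding first-order absorption (ka = 1/h, assumed) changes little: after two doses the ratios are 0.93, 0.79, 0.66 and 0.58.

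**MRT and Vss/F.** In that one-compartment oral case, MRT after two doses is 0.99 of true at all four half-lives, and Vss/F follows CL/F (0.93, 0.78, 0.65, 0.58).

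A biphasic profile behaves differently. Assume 10% of AUC in a 24 h phase and 90% in a 2 h phase, with single-dose AUC set to 1:

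- True MRT = (0.1 × 24 + 0.9 × 2)/ln 2 = 6.06 h.
- After two doses the slow part is multiplied by 1.5 and the fast part by about 1.0002, so AUC0-inf = 0.150 + 0.900 = 1.050.
- CL/F ratio = 1/1.050 = 0.95.
- Written MRT = [(0.150 × 24 + 0.900 × 2)/ln 2]/1.050 = 7.42 h, a ratio of 1.22.
- Vss/F ratio = 0.95 × 1.22, about 1.17.

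So CL/F and Vz/F are always biased downward, whereas MRT and Vss/F have no single direction.

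**How many doses.** Follow-up on Day 15, at 14 ± 1 days after the last dose, puts the last dose at 15 − 14 = Day 1 nominally, or 15 − 13 = Day 2 with the visit tolerance. If the ±24 h analysis window is added, it is 16 − 13 = Day 3 at the latest. SAP 9.3 agrees: its Part 3 visits are Screening, Day −1, Days 1 to 3 and Day 15.

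**Would AUC0-tau alone repair it?** Only at steady state. Before that, AUC0-tau is (1 − q^n) of the single-dose AUC0-inf, so Dose/AUC0-tau is 1/(1 − q^n) times true CL/F. After two doses that is 1.07, 1.33 and 2.00 at 12, 24 and 48 h. At steady state it is right: on the biphasic profile above, AUC0-tau equals the single-dose AUC0-inf, and MRT = [AUMC0-tau + tau × (AUC0-inf − AUC0-tau)]/AUC0-tau returns the true 6.06 h.

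**The case against.** The strongest reply is that no usable last-dose profile may exist. Read nominally, a Day 15 follow-up means a single dose, for which the written formulas are exact. Three further points support this. SAP 9.3 lists no last-dose visit for Part 3. SAP 8.3.1 names only all-days and Day 1 mean plots for the multiple-dose group. SAP 8.3.3 limits dose proportionality to single dose, although the protocol planned a last-day analysis. The multiple-dose list is also qualified by its closing words, so the SAP does not commit to these values whatever the dosing. Most of this stands, and it is why the point is minor. It is not proof: the SAP never states the number of doses, and Protocol 5.2.4.2 has withdrawn subjects attend follow-up as soon as possible. The qualifier governs whether a parameter is calculated, not which formula is used.

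Two stronger readings are tempting and not supported:

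- *The Part 3 clearances are wrong by the steady-state factor.* With the planned 14 daily doses the ratios would be close to 0.94, 0.75, 0.50 and 0.29. The visit tables point to three doses at most.
- *The SAP clearly still intends these values.* Last-dose windows in SAP 7.2 and Day 14 rows in Appendix 1 remain, and SAP 10, which opens "The planned analyses below were not done", does not name the four parameters. But grey shading is lost in this copy, text for the never-enrolled Parts 4 and 5 also remains, and SAP 10 is incomplete: it omits the protocol's Part 3 dose-proportionality and trough-ratio analyses, which SAP 8.3 no longer contains. The Kel rule shows only that the written formulas need Kel, which fits rows meant for single dose equally well.

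**Conclusion.** Wrong as written, and minor. The four rows are correct for a single dose and for Day 1, but the SAP does not limit them to that use while listing the same parameters after multiple dosing.

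The size depends on facts the documents do not give. With one Part 3 dose there is no error. With two or three, last-dose CL/F and Vz/F would be about 0.94 of true at a 6 h half-life, falling to 0.59 (two doses) or 0.45 (three) at 48 h, assuming linear one-compartment kinetics. MRT and Vss/F may shift in either direction.

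The reach is one cohort of 8 randomised subjects, including those on placebo, and descriptive listings and summaries only. Day 1 values, LF and RA are unaffected, and no test or decision rule uses last-dose CL/F.

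**What to change.** 1. In Appendix 1, label the CL/F, MRT, Vz/F and Vss/F rows as applying to single dose and Day 1 only.
2. State in SAP 3.1.2 or 3.3.2 how many Part 3 doses were given. If only one, mark the multiple-dose list in SAP 2.2.2 as not applicable; with the label in item 1, nothing more is needed.
3. If more than one was given, state that these four parameters are not reported from a last-dose profile unless steady state was reached.
4. Only in that case, add these rows: CL/F = Dose/AUC0-tau; Vz/F = (Dose/AUC0-tau)/Kel; MRT = [AUMC0-tau + tau × (AUC0-inf − AUC0-tau)]/AUC0-tau; Vss/F = CL/F × MRT. Appendix 1 then also needs a row defining AUC0-tau.

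The cost is SAP wording. AUC0-tau is already a listed parameter and no new data are needed.
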